6.0 Process Evaluation

For the purpose of this study, we will largely follow the indicators currently used in the national smart care system and the community ART model core indicators in section 5. Standard reports documenting this will be generated and reviewed by the study team and discussed with field teams at monthly management meetings and appropriate corrective actions implemented.

A consolidated report will be generated monthly which will be reviewed by the entire study leadership team on regular scheduled calls. A quarterly report will be developed to share with the national community ART steering committee, Ministry of Health and other implementing partners. This is to ensure transparency, accountability of patient clinical management, antiretroviral therapy management, adherence support and logistic supplies.

Site visits will be conducted by the in-country leadership to review procedures on the ground and implement any corrective action.

7.0 Statistical Analysis

The analysis will compare each of the two trial intervention arms with the “standard-of-care” (control arm), and the primary endpoint is viral suppression at 12 months after study enrolment. The analysis will be done using standard methods for a cluster- randomized trial with a non-inferiority design.

The study has been designed to a study power of between 73 -94% to demonstrate that a trial intervention arm is not inferior to the “standard-of-care” arm for the percentage of participants who are virologically suppressed at 12 months after study enrolment. The definition of “not inferior” is that the percentage of study participants who have died, or are alive but not virally suppressed, at 12 months after enrolment in a trial intervention arm is $\leq 5\%$ higher than in the standard-of-care arm.

Based on the data from the annual first round of the CHiP intervention in the main trial, the number of adults who are known by the CHiP teams to be HIV-positive and to be taking ART at the time of the most recent CHiPs follow-up visit averages approximately 50 per zone, with a harmonic mean of approximately 36 per zone. Assuming that 80% of such adults agree to participate in the study and have not moved out of the community within 12 months after enrolment, the number of study participants per zone who can contribute to the primary endpoint measurement will have a harmonic mean of approximately 30.

Study power calculations have been done with the assumption that an average of 30 study participants per zone will contribute to the measurement of the primary endpoint; that 35 zones are randomized to the 2 intervention arms and 34 zones to the “standard-of-care” arm; and that among study participants in the “standard-of-care” the percentage who have died, or are alive but *not* virally suppressed, 12 months after enrolment to the study is in the range 10-15%. It is also assumed that the coefficient of variation k , of the variation across zones in the percentage of study participants who have either died or are alive but *not* virally suppressed at 12 months after study enrolment, is in the range 0.25 to 0.3. If the percentage of participants who have died or are alive but are *not* virally suppressed at 12 months after study enrolment is 10% in the “standard-of-care” arm, and $k=0.25$ or $k=0.3$, study power is 93% and 91% respectively to show that a trial intervention arm is not inferior to “standard-of-care”. The corresponding study power figures are 78% and 74% if the percentage of participants who have died or are alive but are *not* virally suppressed at 12 months after study enrolment is 15% in the “standard-of-care arm”.

Table summarising study power to show that community ART provision is not inferior to standard-of-care, in terms of patient viral suppression 12 months after either enrolling into community ART or continuing with standard-of-care at the clinic

Standard of care, % not virally suppressed at 12 months after enrolment	Intervention, % not virally suppressed at 12 months after enrolment	Coefficient of variation k	Number of participants per cluster	Study power (%)
5%	$\leq 10\%$	0.25	30	99%
10%	$\leq 15\%$	0.25	30	93%
15%	$\leq 20\%$	0.25	30	78%
5%	$\leq 10\%$	0.30	30	99%
10%	$\leq 15\%$	0.30	30	91%
15%	$\leq 20\%$	0.30	30	74%

We will also use qualitative and quantitative methods to evaluate the acceptability and feasibility of the two models of ART delivery and the barriers to access in care. Interviews would look at the trajectory of linking to care, reflecting on the HIV pathways and care choices prior to the intervention and after and exploring their comparative experience with satisfaction of care and

patient rights, HIV related stigma, household and other social relationships, livelihood pursuits and wellbeing.

The main focus of the economic analysis will be the cost of the models including equipment, materials, laboratory tests and personnel. Cost estimates will be collected for each of the resource items identified from the case report forms and study records. All cost data will be presented in Zambian Kwacha and in US\$. Data will be entered and cleaned in excel. Patient specific resource use data will be coupled with the unit cost estimates to generate a patient specific cost estimate. Mean patient costs will be calculated separately for study intervention arms and standard statistical analysis undertaken. Data analysis will be performed in both Microsoft (MS) excel and Stata-version 13.0.

A cohort model will be developed combining the costs and benefits from the intervention. This approach will provide a conservative estimate of the cost-effectiveness of the intervention, as it will only consider the direct health benefits of the trial participants and not account for the indirect health benefits (such as QALY gains or DALYs averted from the secondary infections avoided).

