Study population: A prospective cohort of adult patients enrolled into ART care in two urban communities participating in the HPTN 071 (PopART) trial. The intervention packages will be implemented throughout the two communities.

Study Size: Intervention will be implemented in 2 communities (Chipata and Kanyama), which have a total of 104 community health worker (CHiP) zones. Within each community, the CHiP zones will be randomized to one of the 3 trial arms. In the community with 54 zones, 18 zones will be randomized to each of the 3 trial arms. In the community with 50 zones, 17 zones will be randomized to the two "intervention" arms and 16 zones will be randomized to the "standard-of-care" arm.

Based on data from the first annual round of the CHiP intervention, the number of adults who are known by the CHiP teams to be HIV-positive and to be taking ART at the time of the most recent CHiP follow-up visit averages 50 per zone, with a harmonic mean of 36 per zone. Assuming that 80% of such adults agree to participate in the study and have not moved out of the community within 12 months after enrolment, the number of study participants per zone who can contribute to the primary endpoint measurement will have a harmonic mean of 30.

Study Arms/Interventions:

Arm 1: Adherence Clubs

- Patients living in these zones will be offered the choice of either being part of an adherence club or to continue receiving care at the clinic. In this model, adherence clubs will consist of a group of 20-25 stable patients who receive care in the community. Members of the club will meet every 3 months at an agreed communal venue where they will receive adherence support, symptom screening and pre-packed medications. Club members will be required to have 2 clinical visits (every 6 months) in a year for their routine clinical review and laboratory monitoring.

Arm 2: Home-Based ART delivery

- Patients living in these zones will be offered the choice of home ART delivery by the CHiP or to continue receiving care at the clinic. This model will provide ART to clinically stable patients in their homes. The CHiPs will visit the participant's homes once every 3 months to provide adherence support, symptom screening and dispense pre-packed drugs to the participant. The participant will only be required to visit the clinic twice in a year for routine clinical review and laboratory monitoring.

Arm 3: Control Arm

- Patients will continue receiving care at the local clinic.

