In this approach, a group of clinically stable patients meet once every 2 or 3 months at a health facility or a community venue. This model allows for peer support and health education among its members. Essential tasks such as weighing patients, symptom screening, adherence support and pre-packed ART distribution are carried out by a peer educator and/or lay counsellor who acts as a club facilitator. This enables patients to visit the clinic once or twice a year for their clinical consultation and routine laboratory monitoring. Patients reporting symptoms or found to be missing their club appointments are referred back to the clinic for assessment. This model is well adapted in urban settings where time spent at the clinic is an issue for patients (41, 42). Adherence clubs were piloted in Khayelitsha, South Africa in 2007 as a way to decongest the clinics. These clubs comprised of approximately 30 stable patients and met every second month with a CHW or a nurse for the club session. Data from this pilot showed that 97% of patients were retained in care and the risk of LTFU was reduced to 57% (43, 44). Since 2012, Medicines' Sans Frontiers' (MSF) piloted an extension of this model into the community and by 2013, have collaborated with the Provincial Government of the Western Cape in implementing 776 adherence clubs representing 19% of all ART patients in care in the metropolitan area(42). The implementation of these community-based adherence clubs (CACs) at a large, public sector facility in peri-urban Cape Town had more than 2000 stable patients down referred from primary health care facilities to CACs and overall retention was 97% at 6 months and 94% at 12 months (46). These findings support the continued expansion of community-based models of ART delivery in high prevalence resource settings.

2. Community ART Groups (CAGs)

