4.0 Study Outcomes

The primary and secondary objectives for this study are listed in Section 2.2. The outcome measures for these objectives are listed below and will be measured in all study arms unless otherwise noted.

A. Primary Outcome – viral suppression at 12 months measured using the standard of care viral load testing equipment currently in place. Viral suppression will be defined according to National guidelines

B. Secondary Outcomes - these will include:

1. ***Viral suppression at 24 months*** – undetectable HIV viral load 24 months after entry into the models of care. This will be done as part of routine laboratory monitoring and measured using routine programmatic data.

2. ***Retention in care / Loss to Follow-up*** -Loss to follow-up from ART programmes describes all patients who are no longer in care and have an unknown outcome. A most useful definition of “loss to follow-up” should refer to patients with unknown outcomes(49). For this study, LTFU will be defined as “*no patient contact for 90 days or longer after the last given appointment*”.

Retention in care refers to *all patients retained in the HIV program*. Patients who are no longer retained in care with unknown outcomes will be classified as LTFU.

- In this study, retention will be defined as the number (%) of clients who are retained in the program at 6, 12 and 24 months after implementation of the intervention.
- The time to Lost to follow-up will be calculated in months according to the time interval between the dates of entry into the intervention to drop out, as recorded in the routine programmatic data.
- Proportion of patients that returned to mainstream care at 6, 12 and 24 months.

3. **HIV disease progression** – defined as having a new or recurrent WHO stage 3 or 4 condition after 6 months of ART, or a fall in CD4 count, (1). For patients with baseline CD4 count of < 200 cells/ μ l a fall of CD4 count to baseline or below after 6 months of ART; or persistent CD4 count < 100 cells/ μ l after 6 months of ART. (2). For patients with baseline CD4 count \geq 200 cells/ μ l, a persistent decline in CD4 count after two or more tests. For this study we will determine the following using routine health centre data:

- Proportion of patients who have had their CD4 count tests done at 6, 12 and 24 months after entering the models of care
- Proportion patients who developed a WHO stage 3 or 4 condition at 6, 12 and 24 months

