- Next community and clinic visit appointment

Data captured electronically during community visits will be linked to the HIV care databases at the health centre. The study team will work closely with the Ministry of Health and implementing partners

supporting the sites to collect relevant data from both the supply and demand side. Data that will be captured electronically during the club and home visits will be synced at the end of the day with the health care centre database. This is to ensure that indicators used for routine monitoring and follow-up will be entered in the current smart care system at facility level. The table below summarizes the core indicators that will be collected at both facility and community levels for the purpose of monitoring and evaluation.

Table 6: Common indicators for community ART models

Common Indicators for Community ART Models of Care		
Main	Core Indicator	Data Source
1. Recruitment	Proportion of patients enrolled into Home-Based ART models by sex	Smart care / HMIS
	Proportion eligible but refused	Consenting register
	Proportion of patients dropping out (within 1,3,6 and 12 months)	Routine data/ Programmatic data
	CD4 count at enrolment	Smart care
	Time on ART before enrolment	Smart care
2. Retention	Number (%) of clients retained at 1,3,6,12 and 24 months	Smart care
	Loss to follow up by reason:	Smart care
	
 • Dead • Transfer • Lost 	
	Number of patients returned to mainstream care (@ 3, 6, 12, 24 months)	Smart care
3. Laboratory	% of clients who developed an OI @ 3, 6, 12 and 24 months	Smart care and routine programmatic data
	Proportion of patients who have had viral loads within the last 6 months	Smart care and routine programmatic data
	Proportion of patients who have had CD4 count in the last 6 months	Smart care and routine programmatic data
	Proportion of patients with viral suppression at 12 and 24months	Smart care and routine programmatic data
4. Drug Supplies	Proportion of patients with CD4 count below 500 in the last 12 months despite treatment	Smart care and routine programmatic data
	Number of individuals missing at least one refill in the last 6 and 12 months	Smart care and routine programmatic data

Additional data collected for measuring the outcomes of the study objectives will be collected from patient clinical records. The key clinical indicators will be collected from smart care and HMIS and these includes:

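### The power table's 30 participants per zone does not follow from the protocol's own inputs: 0.80 x 36 is 28.8, with nothing taken off for participants who have no 12-month viral load

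*Protocol*

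**What the plan says.** The Protocol Summary (Study Size) and Section 7.0 give the same derivation. The base is adults known to be on ART from the first CHiP round: about 50 per zone on average, harmonic mean 36. One reduction is applied, namely that "80% of such adults agree to participate in the study and have not moved out of the community within 12 months" after enrolment. Section 7.0 concludes that "the number of study participants per zone who can contribute to the primary endpoint measurement will have a harmonic mean of approximately 30"; the Summary says the same without the qualifier. The power paragraph then assumes that "an average of 30 study participants per zone will contribute to the measurement of the primary endpoint", with 35 zones in each intervention arm and 34 in standard of care.

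The margin is 5 percentage points on death, or being alive but not suppressed, at 12 months. Stated power for k = 0.25/0.30 is 99/99% at 5% control failure, 93/91% at 10% and 78/74% at 15%.

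Section 4.0 takes the primary outcome from routine care: "viral suppression at 12 months measured using the standard of care viral load testing equipment currently in place". The same section defines loss to follow-up as "no patient contact for 90 days or longer after the last given appointment" and makes it a secondary outcome.

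**The concern.** There are two gaps between the inputs and the 30.

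- **Arithmetic.** 80% of 36 is 28.8. Reaching 30 needs 83.3%, so the rounding goes upward and adds participants.
- **Missing step.** The 80% has two conditions, agreeing and not moving away. Deaths need no allowance, because they count as failures. But a participant who remains in the community and is out of contact, or is in care without a viral load near month 12, has no known outcome and is still counted as contributing.

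At stake is whether the printed power describes the trial that these inputs would deliver. The 104 zones are fixed, so a smaller number per zone cannot be offset with more clusters.

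**Working it through.** **Inputs from Section 7.0:** 35 and 34 zones; margin 0.05; failure rate p of 5%, 10% or 15%; k of 0.25 or 0.30; m participants per zone. Alpha is not stated. Two-sided 5% (critical value 1.96) with equal true rates in both arms is inferred because it reproduces the table.

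**Formula:** variance per zone V = p(1-p)/m + (kp)^2; SE = sqrt[V(1/35 + 1/34)], where 1/35 + 1/34 = 0.05798; power = Phi(0.05/SE - 1.96).

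**Step 1, the plan's own figures (m = 30).** For p = 10%, k = 0.25: V = 0.09/30 + 0.025^2 = 0.003625; SE = 0.01450; 0.05/SE = 3.449; power = Phi(1.489) = 93.2%. The other cells are in the first row below. Cut to whole percentages, all six equal the printed 99/99, 93/91 and 78/74.

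**Step 2, the stated chain.** 0.80 x 36 = 28.8; 30/36 = 83.3%.

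**Step 3, an allowance for no 12-month result, excluding such participants equally in all arms.** m = 28.8 x (1 - L). The protocol gives no value of L, so two are assumed from retention figures cited in its Section 1.1:

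- L = 6%, from the community adherence clubs, where "overall retention was 97% at 6 months and 94% at 12 months": m = 27.1.
- L = 25%, from the 75% 12-month retention cited for general ART programmes: m = 21.6. A later review cited there gives 80%.

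| m per zone | 5% failure (k = 0.25/0.30) | 10% failure | 15% failure |
|---|---|---|---|
| 30 (as used) | 99.9/99.8% | 93.2/91.4% | 78.8/74.6% |
| 28.8 (stated inputs) | 99.8/99.8% | 92.4/90.5% | 77.6/73.4% |
| 27.1 (6% missing) | 99.7/99.7% | 91.1/89.2% | 75.7/71.6% |
| 21.6 (25% missing) | 99.0/98.8% | 85.1/83.1% | 68.0/64.5% |

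Last cell, for example: V = 0.1275/21.6 + 0.045^2 = 0.007928; SE = 0.02144; 0.05/SE = 2.332; power = Phi(0.372) = 64.5%.

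**Step 4, where 80% is crossed.** At 10% failure, 80% power needs m = 18.5/19.6. From 28.8 that is 1 - 18.5/28.8 = 36% or 1 - 19.6/28.8 = 32% without a result. At 15% failure it needs m = 31.2/36.8, which even 30 does not reach.

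**Step 5, the quoted range.** Section 7.0 opens with a power range of 73 to 94%. Its own table for the 10-15% control rates runs from 74 to 93%.

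**The case against.** Several points on the other side stand.

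- **Disclosure.** A reader might infer that the protocol conceals an assumption of complete measurement. It does not: Section 7.0 says that 30 contributors are assumed, and the table repeats the number. What is missing is a factor in how 30 was reached.
- **Rounding.** Section 7.0 says approximately for both 36 and 30, and the difference costs about 1 point.
- **Room in the design.** The 10% rows stay above 80% until about a third of participants lack a result, and the 5% row barely moves. Enrolled patients must be stable and suppressed, so low failure rates are relevant. The 15% rows were below 80% before any loss.
- **Evidence of missing results.** The Table 6 indicator, "Proportion of patients who have had viral loads within the last 6 months", is common monitoring across community ART models and does not show that results will be missing. Laboratory review is scheduled at month 12 in both models (Section 3.1.2), and those who withdraw from an intervention remain in the study (Section 8.2).
- **Loss rates.** The 25% comes from general programmes, not stable suppressed patients, and some loss overlaps with moving away, which the 80% already removes.

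A reader might also infer a much larger loss of power if participants without a result are scored as failures. At m = 28.8, 10% measured failure with 6% lost gives p = 0.94 x 10% + 6% = 15.4% and power of 76.4/72.1%. The documents do not support this as a finding. The loss rate is assumed, it is added to a control rate that may already include loss, and the result sits close to the printed 15% row. The scoring rule may also be in the SAP.

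None of this makes the inputs yield 30, or supplies the missing factor.

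**Conclusion.** The point holds as a minor one. The number per zone under the power table is not what the protocol's inputs give, and no share with a known 12-month outcome is applied. The correction to 28.8 lowers power by about 1 point. Excluding 6% lowers it by about 2 points at 10% failure and 3 at 15%, against the reproduced figures at m = 30. Excluding 25% lowers it by about 8 points at 10% failure and 10 to 11 at 15%. The practical consequence lies mainly in the 15% rows.

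This rests on the inferred two-sided 5% level, on loss rates that are assumptions with 25% as an upper illustration, and on equal loss in all arms. ART numbers may have grown since the first CHiP round, which would raise the base of 36; the documents give no figure. It would go too far to conclude that the trial is underpowered at 5-10% failure.

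**What to change.** In the Protocol Summary and Section 7.0:

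1. Replace 30 with 36 x 0.80 = 28.8, multiplied by an explicit assumed share of participants with a known 12-month outcome (dead, or a viral load result), and give the basis for that share.
2. Recompute all six rows of the power table with that number.
3. Make the opening 73 to 94% range agree with the recomputed table.
4. State whether the assumed 10-15% control rate includes participants lost to follow-up.

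The rule for scoring participants with no result can stay in the SAP. The cost is a recalculation and a few sentences; margin, arms, zones and procedures do not change. The downside is slightly lower stated power, most visibly at 15% failure.

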It is not known whether these models of ART delivery will be feasible in urban low resource settings, or whether the care will be as good as the standard quality of care provided by the health systems, therefore this study is timely and innovative:

(1). This will be a first study in an urban setting in Zambia to rigorously evaluate different models of community ART delivery. This information will be critical for the continued scale up of universal test and treatment and may have cost efficient synergies utilising community HIV test providers.

(2). This study will be a randomized head to head non-inferiority comparison. To this date no studies have shown a comparison in clinical outcomes between the different Community ART models and between them and the current standard of care.

(3). This study will provide policy makers with evidence on operational feasibility, acceptability and cost effectiveness of two models and guide policy on the best models to roll out in the context of UTT.

The Zambian Ministry of Health has identified community models of ART delivery as a way of expanding treatment in the context of universal test and treat. The government, through the National AIDS Council, has engaged several in-country partners and researchers to pilot different community models of ART delivery in order to generate information required to inform model standardization at national level for wider roll-out. These models of care will only include stable adult ART patients, defined as patients on ART for more than 6 months who are virologically suppressed.

In addition to providing policy makers with evidence for community ART models, this study will also enhance the objectives of the HPTN071 trial where linkage to care and retention in care are essential for the outcome of the trial. This study will also increase local scientific capacity to conduct implementation research in order to sustain national ART and PEPFAR targets as well as build collaborations between indigenous Zambian non-profit organizations, the University of Zambia (UNZA) and Ministry of Health, drawing expertise that will ultimately strengthen Zambian research capabilities.

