	CHIPATA (54 Zones)			KANYAMA (50 Zones)		
	HIV+ clients	Total in care in the clinic	On ART in the clinic	HIV+ clients	Total in care in the clinic	On ART in the clinic
Average per zone	99.3	56	51.3	98.6	56.38	46.7
Range in the zone	33-234	14-155	18 - 143	48 - 213	4 - 143	3 - 102
Min-max						

Each zone is served by 2 CHiPs, therefore 1 CHiP will have an average of 23-25 clients on ART who may need to be provided with ART within the community.

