3.1.1 Study Population

The eligible study population will include all stable HIV infected adult patients (≥ 18 years) on first-line ART residing in the 2 HPTN 071 communities and enrolled in the two primary health centres within the community. Stable patients are defined as those who are on first-line therapy, are on treatment and consistently retained in care for more than 6 months, virologically suppressed and have no other health conditions (e.g. TB, pregnancy and other opportunistic infections) requiring attention of a clinician.

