3.1.3 Inclusion Criteria

All HIV adult patient (≥ 18 years) on first-line ART will be screened for eligibility at the health care facility serving the two communities. The eligibility criteria will include:

- All adult patients who are stable. To be considered “stable” a patient must:
 1. Be on first line treatment for more than 6 months and retained in care
 2. Must be virologically suppressed (according to the current standard of care definition of viral suppression)
 3. WHO stage I and II at the time of screening
- Patient resides within the clinic catchment area
- Willing to provide written informed consent and accept CHiPs intervention.

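### The planned 30 analysable participants per zone makes no allowance for the stable-patient criteria, so the printed power implicitly treats the whole on-ART pool as eligible

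*Protocol*

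**What the plan says.** The cluster size is derived in Protocol section 7.0 and repeated in the Protocol Summary under Study Size. The base is the number of adults known to the CHiP teams as HIV-positive and taking ART, from the first annual CHiP round: mean about 50 per zone, harmonic mean about 36. One reduction follows: "Assuming that 80% of such adults agree to participate in the study and have not moved out of the community" within 12 months of enrolment. The result is that "the number of study participants per zone who can contribute to the primary endpoint measurement will have a harmonic mean of approximately 30"; the Summary says the same without the qualifier ("the number of study participants per zone who can contribute to the primary endpoint measurement will have a harmonic mean of 30"). Section 7.0 then uses 30 per zone in every row of its power table.

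The population to be enrolled is narrower than that base:

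- Section 1.2: the models "will only include stable adult ART patients, defined as patients on ART for more than 6 months who are virologically suppressed".
- Section 3.1.1: first-line patients "consistently retained in care for more than 6 months, virologically suppressed and have no other health conditions" that need a clinician's attention.
- Section 3.1.3: more than 6 months of first-line treatment and retained in care; "Must be virologically suppressed (according to the current standard of care definition of viral suppression"); and "WHO stage I and II at the time of screening".

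**The concern.** The 80% is defined in words as agreement to take part plus not moving away. It leaves no room for patients who are on ART but fail the stability criteria: recent starters, those not suppressed, those on a later line, those at WHO stage III or IV, and those with TB or pregnancy. Nothing else in the protocol reduces the 36. The cluster size is therefore derived for all adults on ART, while the trial enrols a subset of them.

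The power statement is the protocol's only justification of size. In a non-inferiority trial, low power makes an inconclusive result more likely. A reader cannot tell from the text what cluster size the eligibility rules would deliver, or whether the planners considered them.

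**Working it through.** **Inputs (Protocol section 7.0 unless noted).** Pool per zone: harmonic mean 36. Factor: 0.80. Zones: 35 per intervention arm, 34 in control. Margin: 5 percentage points. Control rate p of death or non-suppression: 10% to 15% in the text, with 5% also in the table. Coefficient of variation between zones: k = 0.25 or 0.30. Section 7.0 states neither the significance level nor the true intervention rate. Equal true rates and one-sided 2.5% are inferred because they reproduce the printed figures.

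**Is the base the whole on-ART pool?** Table 2 in section 3.1 gives 51.3 on ART per zone in Chipata (54 zones) and 46.7 in Kanyama (50 zones). (54 × 51.3 + 50 × 46.7)/104 = 49.1, which agrees with the mean of about 50. It is.

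**Formula.** With m participants per zone, V = [p(1−p)/m + k²p²] × (1/34 + 1/35), and power = Φ(0.05/√V − 1.96).

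**Reproducing the plan (m = 30).** For p = 0.10 and k = 0.25:

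- bracket = 0.09/30 + 0.0625 × 0.01 = 0.003625
- V = 0.003625 × 0.05798 = 0.0002102, so √V = 0.01450
- 0.05/0.01450 = 3.449, and Φ(3.449 − 1.96) = 93.2%

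All rows at m = 30, as k = 0.25/0.30:

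| Control rate | Computed | Printed |
|---|---|---|
| 5% | 99.9/99.8 | 99/99 |
| 10% | 93.2/91.4 | 93/91 |
| 15% | 78.8/74.6 | 78/74 |

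The table is right for m = 30. A one-sided 5% level would give 96.4/95.4 and 86.8/83.6 in the 10% and 15% rows, which does not match.

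**Cluster size from the stated inputs.** 36 × 0.80 = 28.8. Reaching 30 exactly needs a pool of 30/0.80 = 37.5 or a factor of 30/36 = 83.3%.

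**Adding an eligible share e, m = 36 × e × 0.80.** The documents give no value for e; those below are assumptions. Power in %, k = 0.25/0.30:

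| e | m | 5% control | 10% control | 15% control |
|---|---|---|---|---|
| 100% | 28.8 | 99.8/99.8 | 92.4/90.5 | 77.6/73.4 |
| 90% | 25.9 | 99.6/99.6 | 90.0/88.1 | 74.2/70.3 |
| 80% | 23.0 | 99.3/99.1 | 87.0/85.0 | 70.3/66.6 |
| 70% | 20.2 | 98.5/98.3 | 82.9/80.9 | 65.6/62.3 |

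At 10% control, power reaches 80% at m = 18.5 (k = 0.25) or 19.6 (k = 0.30), which is 64% or 68% of 28.8.

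**What would offset it, taking e = 80%.** The m = 30 power returns if control failure is 8.1% (k = 0.25) or 8.3% (k = 0.30) instead of 10%, or 12.4% or 12.7% instead of 15%. It also returns if the harmonic-mean pool is 30/(0.80 × 0.80) = 46.9 instead of 36, about 30% larger.

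**The case against.** The strongest case is that nothing shows the trial to be short of power. Five arguments support it.

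- **Rounding.** The inputs are given as approximate, and 28.8 against about 30 is rounding. This stands; alone it costs about 1 point.
- **The pool can grow.** The 36 is a first-round snapshot. Table 2 shows about 99 HIV-positive clients per zone, roughly twice the number on ART, in communities receiving intensified ART provision. Patients newly on ART at the snapshot gain treatment time before enrolment. Screening is at the health facility (section 3.1.5), so it may reach patients the CHiP teams do not know. This also stands: 28.8 is what the stated inputs give, not a ceiling on what could be enrolled.
- **Failure should fall too.** Requiring suppression at entry shrinks the pool but should also lower 12-month failure. Pairing a smaller m with the 15% row is the pessimistic corner. This is fair, although section 7.0 itself plans for 10% to 15%.
- **The analysis may be weighted.** A harmonic mean is the right cluster size for unweighted zone proportions, and the protocol does not fix the method. If zone sizes were lognormal with mean 50 and harmonic mean 36, inverse-variance weighting at 80% eligible would give about 93/91% and 78/73%, close to the printed values. The distribution and the weighting are assumptions.
- **Section 3.1 does not claim that all are eligible.** It says only that "therefore 1 CHiP will have an average of 23-25 clients on ART who may need to be provided with ART within the community", and the word may leaves room.

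These arguments bear on whether power is lost. They do not supply the missing factor, and the protocol invokes none of them in deriving 30.

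A reader might infer that the trial is underpowered, or go further and build an eligible share from national treatment-start figures and a cited cohort's suppression rate. The documents do not support either step. Those figures come from other populations (a national count including children, and rural Uganda) and take no account of treatment time gained between snapshot and enrolment.

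**Conclusion.** The concern holds as an undisclosed assumption in the sample-size derivation. The figure of 30 per zone counts all adults on ART and allows only for consent and out-migration, so an eligible share of 100% is built into every power row without being stated.

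The size of the effect is conditional. If 70% to 90% were eligible with no offset, power would be 81% to 90% at 10% control failure and 62% to 74% at 15%, against printed values of 91% to 93% and 74% to 78%. At 5% it would stay at or above 98%. These ranges rest on assumed eligible shares, equal true rates, an inferred one-sided 2.5% level, and an unweighted analysis with harmonic-mean cluster size. A net loss is not proven. The omission itself is certain, and it should be corrected because the power statement is the only support for the trial's size.

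**What to change.** In section 7.0 and its copy in the Protocol Summary, write the cluster size as pool × eligible share × 80%. Give the source of each factor, and state and justify any pool growth or facility recruitment relied on. Recompute the power table over a range of cluster sizes, for example 20, 23, 26 and 29, keeping the 5%, 10% and 15% control rows. Bring the overall range of 73% to 94% quoted in section 7.0 into line with the result; at present it matches neither the text that follows it (74% to 93%) nor the table (74% to 99%).

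An optional tidy-up is to relabel the intervention column, whose ≤ 10, 15 and 20% entries are the non-inferiority limits, and to state the true intervention rate assumed.

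The cost is one rewritten paragraph in two places and one table. All 104 zones are already in the design, so no extra enrolment is needed. The stated power may look less favourable, mainly in the 15% rows.
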